## 4. ANALYSIS POPULATIONS

Population	Definition / Criteria	Analyses Evaluated
Screened	
 
• All participants who were screened for eligibility
 
	
 
• Study Population
 

Randomized	
 
• All participants who were randomly assigned to treatment in the study.
 
• This population will be based on the treatment the participant was randomized to.
 
• Any participant who receives a treatment randomization number will be considered to have been randomized.
 
	
 
• Study Population
 

Enrolled	
 
• All participants who passed screening and entered the study. Included are run-in failures and randomized participants.
 
• Note: screening failures (who never passed screening even if rescreened) and participants screened but never enrolled into the study (Reserve, Not Used) are excluded from the Enrolled population as they did not enter the study.
 
	
 
• Study Population
 

Safety	
 
• All randomized participants who received at least one dose of study treatment.
 
	
 
• Safety
 

Population	Definition / Criteria	Analyses Evaluated
	
 
• Participants will be analysed according to the treatment they actually received.
 
• Note: Participants who were not randomized but received at least one dose of study treatment should be listed.
 
	
Efficacy	
 
• All participants in the safety population who provided at least two evaluable overnight sputum samples.
 
• This population will be based on the treatment the participant was randomized to.
 
	
 
• Efficacy
 

Pharmacokinetic (PK)	
 
• Participants in the safety population who received at least one dose of GSK3036656 and have at least one evaluable PK sample.
 
• Participants will be analysed according to the treatment actually received.
 
	
 
• PK
 

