#### **7.1.4. Strategy for Intercurrent (Post-Randomization) Events**

The primary treatment effect to be estimated will be the while on treatment effect of initial randomised treatment.

All recorded data up to the time of study withdrawal will be included in the analysis, regardless of discontinuation of study medication.

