**7.1.5.1. Statistical Methodology Specification**

Endpoint

 
• Rate of change in log10CFU per ml direct respiratory sputum samples over the period baseline to Day 14.
 

Model Specification

Model 1:
 
 
• Mixed model repeated measures analysis. Terms in the model:             
 
• Response: log10CFU
 
• Categorical: treatment
 
• Continuous: time, BMI
 
• Interaction: treatment*time
 
• Random: Subject
 
 
 
 
Model 2:
 
In addition, to characterize any bi-linear characteristics a bi- linear Bayesian regression model of the following form will also be fitted:
 $y_i = \begin{cases} \text{normal}(\alpha + \beta_1(t_i - cp), \sigma^2) & \text{if } t_i < cp \\ \text{normal}(\alpha + \beta_2(t_i - cp), \sigma^2) & \text{if } t_i \geq cp \end{cases}$ 
 
• Where cp=change (node) point as determined by the data (separate nodes for each treatment group), and t=time.
 
• The model will include terms for intercept, BMI, treatment, treatment*day before node, treatment*day after node, subject.
 
• This model would utilize uninformative uniform priors for cp and <math>\sigma^2</math> (discrete uniform(2,13) and uniform(0,5) respectively) and uninformative normal priors for the intercept, treatment, baseline log10CFU and BMI (normal(0,var=1000000)). Subject will be a random effect with an uninformative prior (normal(0,var), where var=uniform(0,5)).
 
• The efficacy population will be used for both models.
 
• Data from the standard of care arm will be pooled for the analysis.
 
• Where CFU plate counts are Too Numerous To Count (TNTC) a value of 2500 should be imputed for both models.
 

Model Checking & Diagnostics

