
Model 1: Mixed model repeated measures analysis:
 
 
• An autoregressive 1 covariance structure will be used. In the event this fails to converge alternative covariance structures may be considered such as VC.
 
• The Kenward and Roger method for approximating the denominator degrees of freedom will be used.
 
• Normality assumptions underlying the model used for analysis will be examined by obtaining a normal probability plot of the residuals and a plot of the residuals versus the fitted values (i.e. checking the normality assumptions and constant variance assumption of the model respectively) to gain confidence that the model assumptions are reasonable.
 

 
If there are any departures from the distributional assumptions, alternative models will be explored using appropriate transformed data (e.g. square root).
 
 
Model 2: Bi-linear Bayesian regression model:
 
 
The convergence will be examined using trace plots: All chains' trace plots will be inspected visually, to assess the mixing of each chain. Convergence is indicated when all chains appear to be mixing well and overlapping each other randomly (no chain's convergence is indicated until the chains of all model parameters appear well-mixed).
 
Additional convergence diagnostics, such as Monte Carlo Standard Error divided by the standard deviation of the posterior distribution (MCSE/SD), Gelman-Rubin statistic, effective sample size (ESS) and autocorrelation plots may also be reviewed.
 
The modelling will be subject to independent quality control. The final parameter estimates for the mean slopes and the mean node point should be within two times the Monte Carlo Standard Error (2xMCSE).
 

Model Results Presentation
 
 
Model 1: Summary of the mean daily rate of change, standard deviation and associated 95% confidence interval will be presented for each treatment arm.
 
Model 2: The mean and 95% highest posterior density (HDP) interval of the node, slope parameter before node and slope parameter after node, will be presented for each treatment arm.
 

Subgroup Analyses
 
 
No subgroup analyses are planned for this endpoint.
 

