
Sensitivity and Supportive Analyses
 
 
A sensitivity analysis will be performed (Model 1 only) excluding participants who withdraw from the study before Day 10 and/or who were replaced during the study.
 
Additional covariates (see Section 5.3) will be investigated in an exploratory manner using a mixed model repeated measures analysis. Each covariate will be investigated separately utilizing the model described for the primary endpoint. First the primary endpoint model will be fitted but including the covariate of interest and then the primary endpoint model will be fitted including both the covariate and treatment-by-covariate interaction.
 

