## 12.10.6. Efficacy Figures

Efficacy: Figures					
No.	Population	IDSL / Example Shell	Title	Programming Notes	Deliverable
Efficacy					
2.1.	Efficacy	Non-standard EFF_F1	Line Graph of log 10 CFU Over Time by Treatment	Include separate lines for each dose/treatment group.	DE, SAC
2.2.	Efficacy	Non-standard EFF_F1	Line Graph of Change from Baseline in log 10 CFU Over Time by Treatment	Include separate lines for each dose/treatment group.	DE, SAC
2.3.	Efficacy	Non-standard EFF_F2	Individual Subject Profile Plots of log 10 (CFU) Count Over Time by Treatment	Include CFU(0-14) regression line and 95% CI. Separate figure for each treatment group.	SAC
2.4.	Efficacy	Non-standard EFF_F3	Line Graph of Dose vs log 10 CFU (0-14) Slope	Include regression line and 95% CI	DE, SAC
2.5.	Efficacy	Non-standard EFF_F1	Line Graph of TTP Over Time by Treatment	Include separate lines for each dose/treatment group.	SAC

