**12.10.12. Non-ICH Listings**

Non-ICH: Listings					
No.	Population	IDSL / Example Shell	Title	Programming Notes	Deliverable
Protocol Deviation					
32.	Safety	DV2	Listing of All Non-Important COVID-19 Related Protocol Deviations		SAC
Adverse Events					
33.	Safety	PAN12	Listing of COVID-19 Assessments and Symptom Assessments for Subjects with COVID-19 Adverse Events		SAC
Pharmacokinetic					
34.	PK	PK07	Listing of Plasma Pharmacokinetic Concentration-Time Data		SAC
35.	PK	PK13	Listing of Derived Plasma Pharmacokinetic Parameters		SAC
Efficacy					
36.	Efficacy	Non-standard EFF_L1	Listing of Sputum Counts	Include CFU, log 10 CFU and TTP	SAC
37.	Safety	Non-standard EFF_L2	Listing of Mycobacterial Data		SAC
38.	Safety	Non-standard EFF_L3	Listing of Drug Susceptibility Data at Screening		SAC
All Laboratory					
39.	Safety	Non-standard SAFE_L1	Listing of Troponin Data		SAC

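### SAP Model 1 has no random subject slope and does not place its AR(1) term, so the 95% CI for EBA CFU0-14 may misstate precision by an amount the documents do not fix

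*SAP*

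**What the plan says.** SAP section 7.1.5.1 introduces Model 1 as "Mixed model repeated measures analysis. Terms in the model". The response is log10 CFU, treatment is categorical, time and BMI are continuous, treatment-by-time is the interaction, and subject is the only random term. On the covariance it says "An autoregressive 1 covariance structure will be used. In the event this fails to converge alternative covariance structures may be considered such as VC". Degrees of freedom are Kenward-Roger. The steady-state and dose-proportionality models in SAP section 9.1.5.1 state that their structure applies to the G matrix. Model 1 carries no such statement.

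The reported result is defined as follows: "Model 1: Summary of the mean daily rate of change, standard deviation and associated 95% confidence interval will be presented for each treatment arm". It appears in Table 2.3, which is produced for both the dose-escalation efficacy analysis and the final analysis.

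Participants with few samples stay in. The efficacy population is "All participants in the safety population who provided at least two evaluable overnight sputum samples", and section 7.1.4 adds "All recorded data up to the time of study withdrawal will be included in the analysis, regardless of discontinuation of study medication".

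The remaining checks are residual plots for normality and constant variance, exploratory covariates, and one change of analysis set: "A sensitivity analysis will be performed (Model 1 only) excluding participants who withdraw from the study before Day 10" (or who were replaced). Figure 2.3 carries the note "Include CFU(0-14) regression line and 95% CI. Separate figure for each treatment group", and Listing 36 is a "Listing of Sputum Counts".

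**The concern.** The primary endpoint is a slope. A model whose only subject effect is an intercept lets participants start at different bacterial loads but assumes that everyone in an arm shares one true kill rate. If true rates differ, the variance of an arm's mean slope contains a between-participant component that does not shrink as more samples are taken per person. Model 1 has no parameter for it. Residual AR(1) absorbs part of it but not all, and Kenward-Roger cannot restore a variance component that was left out.

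The specification is also ambiguous. Two programmers could both follow the text, one fitting a random intercept with AR(1) residuals and the other AR(1) alone, and their intervals could err in opposite directions.

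Protocol section 10.1.1 plans no formal hypothesis testing, so the per-arm slope and its interval are the primary result. What is at stake is the precision stated for each dose, in arms that may hold as few as 9 participants, including at the look that protocol section 11 intends for dose optimisation and internal decisions.

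**Working it through.** **1. The plan's own figure.** Protocol section 10.1.2 gives about a 90% chance of a negative observed mean with a true change of -0.06, SD 0.15 and n = 9. Check: Φ(0.06 / (0.15/√9)) = Φ(1.20) = 0.885. The original design, SD 0.2 and n = 15, gives Φ(1.16) = 0.877. Both are consistent with the text. Neither speaks to the coverage of Model 1, for which the documents give no figure.

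**2. What the observed SDs contain.** Section 10.1.2 reports SDs of (Day 14 minus baseline)/14 of 0.049 (standard of care, N = 9), 0.067 (5 mg, N = 15) and 0.053 (15 mg, N = 13). Baseline averages two samples, so with independent residuals of SD σ and true slope SD τ:

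SD² = τ² + 1.5σ²/196.

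The documents give neither τ nor σ. Example: SD 0.053 with σ = 0.4 gives τ = √(0.002809 - 0.001224) = 0.040. Setting τ = 0 gives σ = SD × √(196/1.5), which is 0.56, 0.61 or 0.77. Nothing in the documents excludes those values.

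**3. One case worked through.** Take SD 0.060 and assume half its variance is true slope variation: τ = 0.060 × √0.5 = 0.042 and σ = √(0.0018 × 196/1.5) = 0.48. The large-sample ratio of model SE to true SE, for a random intercept plus residual AR(1), is 0.75. Coverage is 2Φ(1.96 × 0.75) - 1 = 0.86. With shares of 0, 25 and 75% the ratios are 1.02, 0.86 and 0.68, and coverage is 95, 91 and 82%.

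**4. Simulation, independent residuals.** REML fits used arms of 19/15/15/9/9/9, true slope 0, and Days 0, 1, 2, 3, 4, 6, 8, 10, 12 and 14 (protocol Schedule of Activities, footnote L). Assumed: intercept SD 0.8, equal slope SD across arms, 10% of participants stopping early, and 5% of other post-baseline samples lost, independent of response. There were 300 runs per scenario, with t on 70 df in place of Kenward-Roger. Coverage of the nominal 95% CI, random intercept plus residual AR(1):

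| SD in 10.1.2 | σ = 0.3 | σ = 0.4 | σ = 0.5 |
|---|---|---|---|
| 0.049 | 83.1% | 86.4% | 92.7% |
| 0.053 | 82.2% | 84.8% | 89.4% |
| 0.067 | 83.2% | 81.9% | 85.3% |

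If slopes do not differ, coverage is 94.6-95.6%. A large-sample calculation with complete data gives 82-92% over the same grid.

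**5. Serial correlation.** Independence between days is itself an assumption. With τ re-set so that the SDs of section 10.1.2 are still matched, large-sample coverage is about 86-94% at an assumed correlation of 0.3 per day, 89-95% at 0.5 and 91-95% at 0.7.

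**6. Other structures, independent residuals.** With AR(1) in place of the random intercept, coverage is 97-100%, and the model SE is 1.1-1.9 times the true value in simulation (1.2-2.1 in the large-sample calculation). The VC fallback gives 63-92% when slopes differ.

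**7. With a random slope.** In the simulation of step 4, random intercept and slope with unstructured G gives 94.3-95.7% when slopes differ and 95.4-96.2% when they do not. In the latter case G is on its boundary in 67-69% of trials. Uncorrelated intercept and slope, dropping the slope only when its variance is estimated as zero, gives 94.4-95.6% and 95.3-95.8%.

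**8. Consequence.** Under the natural reading with independent residuals, an inactive arm's CI lies wholly below zero in 3.7-9.7% of trials, against 1.9-2.9% with a random slope (nominal 2.5%). Mean bias is at most 0.0008 log10 per day in any mixed model. A true -0.06 lies 2.6-4.3 true SEs from zero in an n = 9 arm.

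**The case against.** The strongest reply is that neither size nor direction is established. The documents support any effect from none upward: if residual SD is 0.56 to 0.77 the slopes need not differ and the interval is nominal, and serial correlation, which the choice of AR(1) allows for, pulls coverage back toward 95%. If AR(1) replaces the random intercept, the interval is generally conservative. All of this stands, and it limits the point.

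It is also said that a reader can check. Table 2.2 reports n, mean and SD of change from baseline at Day 14, so mean/14 ± t × SD/(14√n) gives a completers' interval that includes slope variation. That is true and useful, but it would only reveal a problem; it does not correct the interval in Table 2.3. Model 2 does not correct it either, since its slopes are also by treatment with only a subject random effect.

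VC is named only as an example of a fallback, which is fair, but no other is named.

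Three stronger readings are tempting. One is that the primary interval is known to be too narrow, at 82% coverage. That is the low end under independent residuals and one reading of the text. Another is that SDs of 0.049 to 0.067 show that kill rates differ. They mix slope variation with measurement error and cannot show it. The third is that ineffective doses would be carried forward. No test or threshold uses the interval, and the slope estimates themselves are essentially unaffected.

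**Conclusion.** The point holds as a matter of stated precision. Model 1 targets a slope without a random subject slope, and its covariance is under-specified. Under the natural reading the 95% CI for EBA CFU0-14 is too narrow if true slopes differ and about nominal if they do not. If AR(1) replaces the random intercept, it is generally too wide. The coverage ranges rest on assumed residual SD, intercept SD and serial correlation, and apply to CFU0-14 only. An effect of -0.06 would still usually be seen. This is worth correcting before the analysis because the interval is what the primary result reports, but it does not put the design or the point estimates in doubt.

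**What to change.** - State in section 7.1.5.1 that the subject term is a random intercept, and whether AR(1) applies to the residuals.
- Fit a random subject intercept and random subject slope on day (unstructured G, Kenward-Roger) as Model 1. If Model 1 stays as written, prespecify this fit as a sensitivity analysis reported beside it in Table 2.3.
- Replace VC as the named fallback with uncorrelated random intercept and slope, dropping the slope only if its variance is estimated as zero. The boundary rate in step 7 is why this must be written down in advance.
- Do not fall back on unweighted per-participant slopes. With incomplete data their true SD was 1.2-3.0 times that of the random-slope model in an n = 9 arm, and 1.2-1.5 participants per trial had no slope at all.

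Two further changes are optional. Defining AR(1) on elapsed days makes little difference: SE ratios are 0.86/0.75/0.68 on days and 0.87/0.76/0.69 on visit index at slope shares of 25/50/75%. Carrying the change to CFU2-14 and the TTP models would be for consistency only, as no figures were worked for them.

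The cost is SAP wording and one model statement. Intervals widen if slopes vary: at SD 0.060 and a 50% share, the mean half-width rises from 0.026 to 0.035 log10 per day. If slopes do not vary, the SE is about 2-4% larger, for example 0.0139 against 0.0135 in an n = 9 arm at SD 0.049.

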## 2.4. Statistical Analyses

The primary endpoint, EBA CFU0-14, will be analysed using a mixed effects model including treatment, day, BMI and treatment-by-day as covariates. Secondary endpoints of EBA CFU0-2, CFU2-14, TTP0-2, TTP0-14 and TTP2-14 will be analysed similarly to the primary endpoint. See Section 7: Efficacy Analyses for further details.

Plasma concentration-time data will be analysed by non-compartmental methods, the following pharmacokinetic parameters will be determined: Maximum observed plasma drug concentration (Cmax), Time to maximum observed plasma drug concentration (tmax), Area under the concentration-time curve from time of dosing to last quantified concentration, regardless of time (AUC(0-t)), Area under the concentration-time curve from time of dosing extrapolated to 24 hours (AUC(0-24)) and Trough Concentration (Cτ). AUC(0-t) or AUC(0-24) and Cmax may be used for assessment of dose proportionality. Trough concentration (Cτ) samples will be used to assess attainment of steady state. See Section 9 for further details.

Safety data, including AEs, clinical laboratory values, vital signs and ECG, will be summarised descriptively according to GSK's Integrated Data Standards Library (IDSL) standards. See Section 8: Safety Analyses for further details.

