#### **7.1.2. Summary Measure**

Mean daily rate of change in  $\log_{10}$ CFU for each treatment group.

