12.10.5. Efficacy Tables

Efficacy: Tables					
No.	Population	IDSL / Example Shell	Title	Programming Notes	Deliverable
CFU					
2.1.	Efficacy	Non-standard EFF_T1	Summary Table of log 10 CFU Counts Over Time		DE, SAC
2.2.	Efficacy	Non-standard EFF_T1	Summary Table of Change from Baseline in log 10 CFU Counts Over Time	Include baseline row similar to LB1 template.	DE, SAC
2.3.	Efficacy	Non-standard EFF_T2	Rate of Change in log 10 CFU by Treatment – Mixed Model Analysis	For dose escalation analysis, calculate EBA CFU(0-14) only. Supportive SAS output to be produced and archived	DE, SAC
2.4.	Efficacy	Non-standard EFF_T3	Node and Slope Parameter Estimates for log 10 CFU by Treatment – Bi-linear Bayesian Model Analysis	For dose escalation analysis, calculate EBA CFU(0-14) only. Supportive SAS output to be produced and archived	DE, SAC
2.5.	Efficacy	Non-standard EFF_T2	Rate of Change in log 10 CFU by Treatment – Mixed Model Analysis – Withdrawn/Replaced Participants Excluded	For endpoints CFU(0-14) and CFU(2-14) only. Supportive SAS output to be produced and archived	SAC
2.6.	Efficacy	Non-standard EFF_T4	Summary of Covariate and Treatment*Covariate Interaction Significance For log 10 CFU(0-14) Mixed Model Analysis	Supportive SAS output to be produced and archived	SAC
TTP					
2.7.	Efficacy	Non-standard EFF_T1	Summary Table of TTP Counts Over Time		SAC

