Example : EFF\_T3  
 Population : Efficacy

Table EFF\_T3  
 Node and Slope Parameter Estimates for log10CFU by Treatment - Bi-linear Bayesian Model Analysis

Endpoint (units)	Treatment	N	n	Mean (95% HPD Interval)		
				Node	Slope Before Node	Slope After Node
EBA CFU 0-14 (log 10 CFU/mL)	<Rifafour>	xx	xx	x.xxx (x.xxx, x.xxx)	x.xxx (x.xxx, x.xxx)	x.xxx (x.xxx, x.xxx)
	<656 Dose 1>	xx	xx	x.xxx (x.xxx, x.xxx)	x.xxx (x.xxx, x.xxx)	x.xxx (x.xxx, x.xxx)
	<656 Dose 2>	xx	xx	x.xxx (x.xxx, x.xxx)	x.xxx (x.xxx, x.xxx)	x.xxx (x.xxx, x.xxx)
	<656 Dose ...>	xx	xx	x.xxx (x.xxx, x.xxx)	x.xxx (x.xxx, x.xxx)	x.xxx (x.xxx, x.xxx)
	<656 Dose 5>	xx	xx	x.xxx (x.xxx, x.xxx)	x.xxx (x.xxx, x.xxx)	x.xxx (x.xxx, x.xxx)
EBA CFU 2-14 (log 10 CFU/mL)	<Rifafour>	xx	xx	x.xxx (x.xxx, x.xxx)	x.xxx (x.xxx, x.xxx)	x.xxx (x.xxx, x.xxx)
	<656 Dose 1>	xx	xx	x.xxx (x.xxx, x.xxx)	x.xxx (x.xxx, x.xxx)	x.xxx (x.xxx, x.xxx)
	<656 Dose 2>	xx	xx	x.xxx (x.xxx, x.xxx)	x.xxx (x.xxx, x.xxx)	x.xxx (x.xxx, x.xxx)
	<656 Dose ...>	xx	xx	x.xxx (x.xxx, x.xxx)	x.xxx (x.xxx, x.xxx)	x.xxx (x.xxx, x.xxx)
	<656 Dose 5>	xx	xx	x.xxx (x.xxx, x.xxx)	x.xxx (x.xxx, x.xxx)	x.xxx (x.xxx, x.xxx)

Bi-linear model including treatment, day, BMI and treatment-by-day before node and treatment-by-day after node as covariates. The Day 2-14 model also includes log baseline CFU as a covariate. Baseline (Day 0) is defined as the mean of Day -2 and Day -1; if data was available at only one of these timepoints then that value was used as baseline.

Example : EFF\_T4  
 Population : Efficacy

Table EFF\_T4  
 Summary of Covariate and Treatment\*Covariate Interaction Significance For log10CFU (0-14) Mixed Model Analysis

Terms in the Model	Numerator Degrees of Freedom	Denominator Degrees of Freedom	F-test	p-value
Age [1]	xx	xx	x.xx	0.xxx
Treatment*Age [1]	xx	xx	x.xx	0.xxx
Creatinine clearance [2]	xx	xx	x.xx	0.xxx
Treatment*creatinine clearance [2]	xx	xx	x.xx	0.xxx
...				

Primary model includes treatment, day, BMI and treatment-by-day as covariates.

[figure not shown]
[1] Primary model fitted first with age, then with age + age\*treatment

[2] Primary model fitted first with creatinine clearance, then with creatinine clearance creatinine clearance\*treatment

...

Example : EFF\_F1  
Population : Efficacy

Table EFF\_F1  
Line Graph of Mean log10CFU Over Time by Treatment

[figure not shown]

Programming note: Include 95% confidence intervals of the slopes.

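### Table 2.6 screens covariates for their effect on the time-averaged level of log10CFU, not on the daily rate of change that is the endpoint

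*SAP*

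**What the plan says.** SAP 7.1.2 defines the primary summary measure as "Mean daily rate of change in" log10CFU for each treatment group, which is a slope.

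SAP 7.1.5.1 specifies Model 1 under "Mixed model repeated measures analysis. Terms in the model". The response is log10CFU, treatment is categorical, time and BMI are continuous, subject is random, and treatment*time is the only interaction. SAP 2.4 agrees: the endpoint "will be analysed using a mixed effects model including treatment, day, BMI and treatment-by-day as covariates".

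For the covariates listed in SAP 5.3, the supportive-analysis part of 7.1.5.1 says "Each covariate will be investigated separately utilizing the model described for the primary endpoint". Step one adds the covariate. In step two "the primary endpoint model will be fitted including both the covariate and treatment-by-covariate interaction".

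The output is Table 2.6 (SAP 12.10.5), "Summary of Covariate and Treatment*Covariate Interaction Significance", titled for the log10CFU(0-14) mixed model. Its shell EFF_T4 gives an F-test and p-value per term and states "Primary model includes treatment, day, BMI and treatment-by-day as covariates", then, taking age as the example, "Primary model fitted first with age, then with age" plus age-by-treatment. Neither the text nor the shell has a covariate*time or treatment*covariate*time term.

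**The concern.** In a model for log10CFU by day, a factor can change the slope only through a product with time. A covariate main effect moves a participant's whole profile up or down, and treatment*covariate does the same by a different amount in each arm. Neither term describes how fast counts fall.

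SAP 5.3 says the screen is meant to judge which covariates matter for possible later analyses. As planned, a covariate tied only to bacterial load at entry could be carried forward as relevant to bactericidal activity. One that truly changes the kill rate could be passed over, or could vanish where its load and rate effects have opposite signs.

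**Working it through.** The plan gives no power or expected result for this screen, so there is no figure of its own to reproduce.

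**1. What the planned term estimates.** Let covariate *x* have load effect λ (on level) and rate effect γ (per day).
- Sampling days are 0, 1, 2, 3, 4, 6, 8, 10, 12, 14 (Protocol section 2, footnote L; Day 0 is the mean of Days -2 and -1). Mean day = 60/10 = 6.0.
- With complete data and a random subject intercept, the coefficient of *x* equals that from regressing participants' mean log10CFU on arm, BMI and *x*. Its expectation is λ + 6.0γ.
- Numerical check on one simulated data set: -0.1439 by both routes. The six arm slopes agreed to five decimals without the covariate, with it, and with treatment*covariate.
- With AR(1) added, the multiplier is 6.0 to 6.7.

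**2. Inputs for an illustration.**
- Documents: up to five cohorts of 12-20, randomised 3:1 (Protocol 5.1, 5.3). Two of 20 and three of 12 give GSK3036656 arms of 15, 15, 9, 9, 9 and pooled standard of care of 5+5+3+3+3 = 19, total 76. Observed SD of (Day 14 - baseline)/14: 0.049 to 0.067 (Protocol 10.1.2).
- Assumed: slope SD 0.035 and residual SD 0.45. These imply √(0.035² + 0.45² × 1.5/14²) = 0.053, inside the observed range. The documents give no intercept SD, so *s* = 0.4 to 0.9 is shown. The covariate is binary at 40% prevalence; tests are two-sided 5%.

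**3. Hand calculation for γ = -0.04/day, λ = 0.**
- Planned test: SD of a participant mean = √(*s*² + 6² × 0.035² + 0.45² × 9.5/10²). The 9.5 allows for Day 0 being a mean of two samples. SE = SD/√(69 × 0.4 × 0.6) = SD/4.07. Signal = 6 × 0.04 = 0.24.
  - *s* = 0.9: SD 0.935, SE 0.230, ratio 1.05, power 18%.
  - *s* = 0.4: SD 0.473, SE 0.116, ratio 2.07, power 53%.
- Covariate*time: Σ(t-6)² = 210. Residual variance of a participant slope = 0.45² × (210 - 18)/210² = 0.00088. SD = √(0.035² + 0.00088) = 0.0459. SE = 0.0459/√(70 × 0.24) = 0.0112, ratio 3.57, power 94%.

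**4. Simulation on the same inputs** (5000 trials per cell; ranges run over *s* = 0.9 to 0.4).

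| True effect | Planned test | covariate*time |
|---|---|---|
| Rate -0.04/day | 18-54% | 94% |
| Rate -0.02/day | 8-17% | 43% |
| Rate -0.04/day, 10% prevalence | 10-25% | 56% |
| Load only, 0.8 log10 | over 90% | 5% |
| Load only, 0.4 log10 | 41-93% | 5% |
| Load +0.24 with rate -0.04/day | 5% | 94% |

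In the last row 0.24 - 6 × 0.04 = 0, so the planned test sees nothing. For slope SD 0.029 to 0.054, the first row becomes 17-54% v 74-98%. With intercept-slope correlation from -0.4 to 0.4 it is 17-68% v 94-95%.

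**5. Covariance for the added term.** False positives of covariate*time at nominal 5% were 12-16% with random subject plus AR(1), 15-25% with random intercept only, and 5-7% with random intercept and slope.

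**6. Three-way term.** At 40% prevalence, with a -0.04/day effect in the GSK3036656 arms only, treatment*covariate*time has 18% power (planned treatment*covariate: 6-9%). All six arms contain both covariate levels in 97%, 59% and 12% of trials at 40%, 20% and 10% prevalence.

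**The case against.** SAP 5.3 does not say the covariates are to be judged by their importance for kill rate. If a later analysis entered one as a main effect, as BMI is now, the planned step would test exactly that term. EFF_T4 also lists its terms openly, so a statistical reader can see that none involves time. Both observations are fair. They make a clear label the minimum remedy, but they do not make a level test informative about a rate endpoint, and the title points to log10CFU(0-14).

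The figures rest on assumed variances and prevalence, and only binary covariates were simulated, although age and creatinine clearance are continuous. The -0.04/day effect is large: two-thirds of the -0.06 that Protocol 10.1.1 treats as a good response to a drug. At -0.02/day even covariate*time reaches only 43%. This limits the gain, but step 1 does not depend on these assumptions.

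A reader might infer three stronger things.
- **That the planned test is blind to rate effects.** It is not. It carries about 6 times the rate effect, mixed with load and judged against between-participant variation in level.
- **That the primary arm slopes are wrong.** Their point estimates are unaffected by this issue. Their confidence intervals depend on the covariance structure, which is a separate question; nothing is claimed about them here.
- **That BMI in Model 1 fails at its job.** The current text lists BMI as a covariate without saying that it corrects the slope. Its rationale appears only in the amendment logs, and a potential influence on the endpoints does not amount to that claim.

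**Conclusion.** The point holds as a minor one. Table 2.6 as specified tests covariates against a time-averaged level of log10CFU, while the endpoint is a daily rate. That follows from the model terms alone. How much it matters depends on the assumptions in step 2, above all the intercept SD, which the documents do not report. Across 0.4 to 0.9, the planned test finds a -0.04/day rate effect in roughly one trial in five to one in two, where covariate*time finds it in about 94%; it also flags a pure 0.8 log10 load difference in over 90%. The table is exploratory and is produced only at the final SAC deliverable. The documents therefore give no ground for reading this as a threat to dose escalation or to the primary result.

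**What to change.** In SAP 7.1.5.1 and shell EFF_T4:
- Fit the primary model plus covariate plus covariate*time, and report the covariate*time test.
- For these exploratory fits only, use a random subject intercept and slope, because leaving out the random slope inflates false positives (step 5). If that fit does not converge, regress participant least-squares slopes on arm and covariate.
- Label any retained covariate and treatment*covariate rows as effects on log10CFU level.
- Treat treatment*covariate*time as optional, and only where every arm contains the covariate levels.

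The cost is SAP wording, one shell edit and one extra fixed-effect degree of freedom per covariate, with no new data. The covariance will differ from Model 1, so the instruction to reuse the primary model needs a stated exception. Rare covariates remain underpowered (56% for -0.04/day at 10% prevalence). HIV and diabetes may be among them, because Protocol 6.2 restricts HIV entry and excludes diabetes from some cohorts. Relabelling alone would make the table accurate but would leave the rate question unanswered.
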